## 5.3. Safety Analysis Set [SAF]

The Safety population will contain all patients who are in the Enrolled population and receive at least one dose of study medication (i.e., monotherapy and/or combination therapy).

## 5.4. Per Protocol Analysis Set [PPAS]

All patients included in the mITT population who do not have any major protocol deviations that could affect the primary efficacy analyses.

Page 19 of 46

## 6. GENERAL CONSIDERATIONS

## 6.1. Reference Start Date and Study Day

Study Day will be calculated from the reference start date and will be used to show start/stop day of assessments and events. It will appear in every listing where an assessment date or event date appears.

Reference start date (Day 1) is defined as the day of the first dose of combination therapy. Day before initiation of combination therapy will be consider from day -28 to day -1.

- If the date of the event is on or after the reference date, then:
- Study Day = (date of event reference date) + 1.
- If the date of the event is prior to the reference date, then:
- Study Day = (date of event reference date).

In the situation where the event date is partial or missing, Study Day, and any corresponding durations will appear partial or missing in the listings.

#### 6.2. Baseline

Unless otherwise specified, baseline is defined as the last non-missing measurement taken same day or prior to reference start date (including unscheduled assessments) before first dose of study medication (monotherapy or combination therapy. Adverse Events (AEs) and medications commencing on the reference start date/time will be considered post-baseline, unless the start time of the AE is known to be prior to the first dosing of the study drug. Since there is no Lab assessment in Visit 2, Lab values collected at Visit 1 will be considered baseline for Lab data. For combination therapy related analysis, the baseline will be the measurements that are taken at Visit 2 (Week 0).

## 6.3. Retests, Unscheduled Visits and Early Termination Data

In general, for by-visit summaries, data recorded at the nominal visit will be presented. Unscheduled measurements will not be included in by-visit summaries. Listings will include scheduled, unscheduled, retest and early discontinuation data.

## 6.4. Windowing Conventions

Visit windowing will be consider as per protocol visit  $X \pm 2$  days for this study.

#### 6.5. Statistical Tests

The default significant level will be (5%); confidence intervals will be 95% and all tests will be two-sided, unless otherwise specified in the description of the analyses.

Page 20 of 46

#### 6.6. Common Calculations

For quantitative measurements, change from baseline will be calculated as:

• Test Value at Visit X – Baseline Value

And for change between Visit 3 and Visit 4 will be calculated as:

• Test Value at Visit 4 – Visit 3 Value

And for change between Visit 4 and Visit 5 will be calculated as:

• Test Value at Visit 5– Visit 4 Value

#### 6.7. Software Version

All analyses will be conducted using SAS version 9.4 or higher (SAS Institute, Cary NC).

## 7. STATISTICAL CONSIDERATIONS

Summaries of continuous variables will include descriptive statistics (number of non-missing observations [n], mean, standard deviation [SD], median, minimum and maximum) and for categorical variables (the number of non-missing observations [n] and percentage), unless otherwise stated in the relevant section. Percentages will be based on the number of patients within the relevant analysis population and treatment arm, or the number of patients with data available where relevant.

If the original data has N decimal places, then the summary statistics will have the following decimal places:

Minimum and maximum: N

Mean, median, Q1, Q3, confidence intervals, ratios: N + 1

[figure not shown]
SD: N+2

Percentages will be reported to one decimal place. P-values should be reported to three decimal places, except values <1.000 but >0.999 will be presented as '>0.999' (e.g., 0.9998 is presented as >0.999); and values <0.001 will be presented as '<0.001' (e.g., 0.0009 is presented as <0.001)

## 7.1. Adjustments for Covariates and Factors to be Included in Analyses

The following covariates and factors are used in the analyses.

- Treatment
- Age (eCRF page: Demography)
- Gender (eCRF page: Demography)
- Body Mass Index (eCRF page: Physical Examination)
- Baseline SBP
- For details of their inclusion in the models, see the specific analysis section

Page 21 of 46

#### 7.2. Multicenter Studies

This study will be conducted by multiple investigators at multiple centers internationally. Center pooling will not be carried out for use in analyses for this study.

## 7.3. Missing Data

All analyses will be performed on observed data. Missing data will not be imputed for this study.

## 7.4. Multiple Comparisons/ Multiplicity

Not Applicable.

## 7.5. Examination of Subgroups

Subgroup analyses will be conducted as stated in the exploratory analysis sections. It should be noted that the study was not designed to detect treatment differences with high statistical power within subgroups.

The following subgroups will be assessed and described within the exploratory analysis sections on ENR and mITT populations respectively.

- Hypertension grade at screening
- CHD
- Presence of diabetes (patients with or without diabetes) at screening
- Presence of hypercholesterolemia (patients with or without hypercholesterolemia) at screening

Hypertension grade at screening is derived as follows;

```
140 <= SBP < 160 or 90 <= DBP <100
160 <= SBP < 180 or 100 <= DBP <110
```

Patients with hypercholesterolemia at screening can be identified based on the clinical significance of the total cholesterol value collected in the blood chemistry laboratory data. If the total cholesterol at screening has clinical significance as per the investigator's input, then the patient will be considered for hypercholesterolemia and the details will be entered in the medical history data.

## 8. OUTPUT PRESENTATIONS

APPENDIX 1 shows conventions for presentation of data in outputs.

The templates provided with this SAP describe the presentations for this study and therefore the format and content of the summary tables, figures, and listings to be provided by IQVIA Biostatistics.

Page 22 of 46

## 9. DISPOSITION AND WITHDRAWALS

All patients who provide informed consent will be accounted for in this study.

## 9.1. Disposition

Patient disposition and withdrawals, including count and percentage of patients screened, screen failures, completed the study, discontinued the study, patient meets newly developed or not previously recognized and reason for discontinuation will be presented for the ENR population from eCRF page End of Study Treatment. Patient who discontinues from the study early will be asked to complete all the assessments of visit 5.

Number of patients in each population, including reasons for exclusion, will be presented for ENR population.

A listing of inclusion and exclusion criteria evaluation (met/not met) will be presented for the Screen Failures using ENR population. Subjects who withdraw prematurely can be part of any population (ENR, mITT or PP) depending on the individual follow-up characteristics and according to population derivation. Data collected on study patients up to the time of withdrawal must remain in the trial database.

If a patient does not meet one or more eligibility criteria required for participation in the trial during the screening procedures (Visit 1) should not be included in the ENR population. The patient disposition table will show the data referring to: Patient Screened (All patients), Patients Screen Failed, Patients Enrolled

Screening Failures: Patients who consented to participate in the clinical trial by signing the ICF, but do not meet one or more eligibility criteria required for participation in the trial during the screening procedures (Visit 1), and subsequently are not assigned to the study treatment (monotherapy) or entered in the study are considered screening failures.

A patient who is in line with all I/E criteria at Visit 1, is enrolled (ENR population) and receive monotherapy, but then the results of the lab tests show that he cannot be enrolled must be considered a drop-out.

In case this study gets suspended or prematurely terminated, written notification, documenting the reason for study suspension or termination, will be provided by the suspending, or terminating party to study patients, Investigators, ECs, Sponsor and Regulatory Authorities with the reason(s) for the termination or suspension. Data will be analyzed till the communication from sponsor/authorities for suspension or termination of the study.

- Possible reasons for early termination or temporary suspension of the study include, but is not limited to:Study closure based on PI decision and/or,
- Study closure based on Sponsor decision and/or
- Study closure based on regulatory or other oversight bodies initiation and/or
- Review of serious, unexpected and related AEs and/or
- Non-compliance

Page 23 of 46

- Lack of efficacy
- Lost to follow up
- Withdrawal by patient
- Patient meets newly developed or not previously recognized

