REVARIN	Glol	oal Medical Department	
	Protocol Template		
Identification Number	Version Number	State	Effective date
FORM-000050125	3.0, CURRENT	Effective	13 May, 2022

- If the patient meets an exclusion criterion (newly developed or not previously recognized) that precludes further study participation.
- Use of any prohibited medication that in the opinion of the Investigator or Sponsor necessitates the patient being withdrawn.

The reason for the withdrawal of study treatment, or withdrawal from the study must be well documented in the source documents and in the eCRF page and should capture the date and the specific underlying reason for discontinuation of study treatment or patient discontinuation/withdrawal.

Patients who discontinue from the study early will be asked, anyway, to complete all the assessments of Visit 5. Patients may discontinue the study treatment, but remain in the study for follow-up, especially for safety study endpoints (if applicable).

If a patient has been discontinued/withdrawn due to an AE, the Investigator must immediately notify the relevant pharmacovigilance contact (see Section 9.9) and should be followed-up until the AE is resolved or the Investigator deems further observations or examinations as no longer medically indicated.

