13 STUDY DISCONTINUATION AND CLOSURE

In case this study gets suspended or prematurely terminated, written notification, documenting the reason for study suspension or termination, will be provided by the suspending, or terminating party to study patients, Investigators, ECs, Sponsor and Regulatory Authorities with the reason(s) for the termination or suspension.

Possible reasons for early termination or temporary suspension of the study include, but is not limited to:

- Study closure based on PI decision and/or,
- Study closure based on Sponsor decision and/or,
- Study closure based on Regulatory or other oversight bodies initiation and/or,
- Review of serious, unexpected, and related AEs and/or,
- Non-compliance.

The Sponsor and the Investigator should take the following steps to follow up on patient safety and ensure data integrity:

- Notify the IEC.
- Contact all patients by phone and distribute written communication that the study has been stopped.
- Advise all patients to report for an early termination visit.
- Make plans to follow all patients for AEs for 2 months after the study has been stopped or for as long as it takes for any AE/SAEs to resolve, whichever is longer.

• Instruct study staff to enter all data in the case report form and ensure their completion. The study patients will be contacted by the PI (or a designee), as applicable, and be informed of changes to study visit schedule.

Adequate measures will be taken to ensure the safety of the patients.

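### If the study is stopped, SAP 9.1 ends the analysed data at the stop notice, before the early-termination visit and adverse event follow-up that Protocol 13 requires

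*SAP*

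**What the plan says.** SAP 9.1 (Disposition) repeats the notification paragraph of Protocol 13 for a study that is suspended or ended early, then adds a data rule: "Data will be analyzed till the communication from sponsor/authorities for suspension or termination of the study". It makes no exception for safety data.

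Protocol 13 (Study Discontinuation and Closure) lists what the sponsor and investigator should do in that event:

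- Patients are told, by telephone and in writing, of the stop.
- On attendance, the instruction is: "Advise all patients to report for an early termination visit".
- Everyone is then tracked for adverse events over a further 2 months, or "for as long as it takes for any AE/SAEs to resolve, whichever is longer".
- On data entry, the instruction to sites is: "Instruct study staff to enter all data in the case report form and ensure their completion".

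Laboratory tests and the 12-lead ECG are scheduled only at Visit 1 and Visit 5 (Protocol 2.2 and 8.2).

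Elsewhere the SAP provides for data from patients who stop early. SAP 6.3 states: "Listings will include scheduled, unscheduled, retest and early discontinuation data". SAP 18.3 to 18.5 summarise an end-of-treatment visit, which for ECG and vital signs includes discontinuation. Appendix 1 has an Early Termination output visit. SAP 18.1 defines treatment-emergent events from the first dose and gives no end date.

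**The concern.** Under Protocol 13, close-out begins once the study has been stopped, and the notice announces that stop. The SAP ends the analysed data at the notice. What the protocol collects during close-out would therefore be recorded and then left outside the analysis.

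The stake is safety reporting. Review of serious, unexpected and related adverse events is one of the stopping reasons listed in both documents. After a stop for that reason, the omitted data would include events that began after the notice, outcomes of events still open, and the early-termination laboratory and ECG results. These are data that a reader of the safety report would particularly want.

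**Working it through.** The plan gives no figure for this rule, so there is none to reproduce. The check compares the texts and then estimates the scale.

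**1. Order of events.** The early-termination visit and the follow-up in Protocol 13 both come after the study has stopped. SAP 9.1 ends the analysed data at the communication of that stop. The 2 months are a minimum, because the longer of the two periods applies.

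**2. Does another SAP rule bring the data back?** None of SAP 6.3, 18.1, 18.3, 18.4, 18.5 or Appendix 1 mentions a study-level stop or overrides 9.1. Taken alone, these provisions would include close-out data, so the SAP is also inconsistent with itself. The cut-off does not appear in Protocol 12 or 13, and SAP 3.3 does not list it as a change from the planned analysis.

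**3. What falls on each side of the cut-off.**

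| Data | Before or after the notice | Under SAP 9.1 as written |
|---|---|---|
| BP at Visits 2, 3 and 4 already attended | before | kept |
| Unscheduled laboratory tests or ECGs already done | before | not cut |
| Early-termination laboratory tests and ECG | after | not analysed |
| Early-termination BP | after | not analysed |
| Later adverse events and outcomes | after | not analysed |

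**4. Patients short of Week 12.** Inputs from the documents:

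- First patient in by September 2023, last patient out by April 2024, and 16 weeks (112 days) per patient (Protocol 2, synopsis).
- SAP v3.0 dated 17 April 2024 (SAP modification history).

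Assumptions: uniform accrual starting on 1 or 30 September 2023, last patient out on 30 April 2024, and visit windows ignored.

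- Accrual ends 112 days before 30 April 2024, on 9 January 2024.
- Accrual length is 130 days from 1 September, or 101 days from 30 September.
- On 17 April 2024, patients enrolled after 27 December 2023 (17 April minus 112 days) are short of Week 12. That leaves 13 days of accrual, from 27 December to 9 January.
- Share = 13/130 = 10%, or 13/101 = 13%.
- On 30 April 2024 the share is about zero.

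This share counts everyone enrolled in that window, including any who had already withdrawn. It is therefore an upper figure for patients still in the study.

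**5. Adverse event time left out for such a patient.** On 17 April 2024 these patients are between 99 days (enrolled 9 January) and 112 days from Visit 1. Taking 2 months as 61 days and follow-up at its minimum, the share of observation time that is not analysed is 61/(elapsed days + 61):

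- 99 days: 61/160 = 38%
- 112 days: 61/173 = 35%

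**6. Primary analysis.** The mITT population requires both Week 0 and Week 12 assessments (Protocol 12.3, SAP 5.2), and by-visit summaries use nominal visits (SAP 6.3). An early-termination BP before Week 12 would add almost nothing to the primary analysis with or without the cut-off.

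**The case against.** The case against is that Protocol 13 governs patient safety and data collection and sets no analysis rule. Collecting data for care while setting an earlier analysis cut-off is not in itself a contradiction. SAP 9.1 does not say that later data will be deleted or left unlisted, and serious events are reported individually whatever the SAP says (Protocol 9.10). SAP v3.0 is dated close to the estimated last patient out, so few patients could be affected.

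Much of this stands, and it limits the point. The protocol does not forbid an analysis cut-off. The difficulty is that 9.1 states one without a safety exception, against the SAP's own general provisions. Individual case reporting does not replace the safety tables.

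A reader might infer more than the documents support:

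- **That BP data are lost.** Readings at visits attended before the notice stay in the analysis. Only the early-termination reading is affected.
- **That patients short of Visit 5 would have no on-treatment laboratory or ECG data.** Protocol 8.2 permits unscheduled assessments and additional ECGs, and SAP 18.4 uses unscheduled ECGs in its analysis of notable changes. Only the scheduled post-baseline results are at issue. Protocol 13 does not say whether patients are still on drug at the early-termination visit.
- **That the Protocol 10 provision is cut off too.** That section says: "Patients who discontinue from the study early will be asked, anyway, to complete all the assessments of Visit 5". It concerns individual discontinuation, and those assessments may well precede any study-level notice.
- **That a large share of patients is exposed.** A stop midway through the trial would give a high share, but such dates precede SAP v3.0, and an edit to v3.0 can affect only a stop after it.

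**Conclusion.** The point holds as a contingent gap in safety reporting. If the study is suspended or terminated, SAP 9.1 read literally excludes adverse events and outcomes after the notice, together with the early-termination laboratory and ECG results, although Protocol 13 requires these data to be collected and entered. In a study that runs to completion, nothing changes.

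The exposed share is about 10–13% of enrolled patients at the date of SAP v3.0, and it runs down to about zero at the end of April 2024. That range rests on uniform accrual, the protocol's estimated dates and 16 weeks per patient; slower enrolment would extend the exposure. The conflict between the texts does not depend on these assumptions. The documents do not support reading this as a threat to the primary efficacy result.

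**What to change.** Replace the sentence in SAP 9.1 with:

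> If the study is suspended or prematurely terminated, all safety data collected up to each patient's last contact, including the early-termination visit and the adverse event follow-up of Protocol section 13, will be included in the safety analyses and listings, with events starting after the communication date flagged. BP from the early-termination visit will be listed and summarised as Early Termination and will not be used as Week 12.

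The flag lets a reader separate events that began before the notice from those that began after it. The change is confined to this one rule and asks nothing new of sites or patients, because the protocol already provides for the visit, the follow-up and the data entry. The cost is that database lock after a stop must wait for the close-out data, which means at least the 2-month follow-up and longer if events are unresolved.

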#### 9.2. Protocol Deviations

All protocol deviations (PD) will be discussed and reviewed on a case-by-case basis before the DBL at the data review meeting. All PDs reviewed by Sponsor will be documented. Individual PDs will be presented in a data listing. The number and percentage of patients with Critical/Major PDs, patient who are excluded from the study will be summarized by deviation on ENR population. PD summary will be classified into "Monotherapy" and "Combination Therapy" based on the incidence date of PD. Additional Critical, Major and Minor PDs may be identified during data review and will be agreed upon with the Sponsor and reflected in the Tables and Listing as appropriate.

All PDs will be recorded and classified in IQVIA Clinical Trial Management System (CTMS) as per CS\_WI\_PL0038, Handling of Protocol Deviations and will be reviewed before the Data review Meeting (DRM). In DRM PDs will be categorized as minor/major/critical. Based on classification of identified PD the PP population will be confirm for the analysis. The process by which the protocol deviation information will be obtained and used is to be discussed and agreed with the customer (refer to WI\_PL0038, Handling of Protocol Deviations). For IQVIA managed clinical trials reference the Protocol Deviations Management Plan (CS\_TP\_PL0064): PDs category are also defined in the Artemisia PDMP.

#### 9.3. COVID-19 IMPACT

The impact of COVID-19 on study related procedures are collected on 'COVID-19 Impact Log' in eCRF. Impact information which includes Assessment/Procedure Impacted, Type of Impact, and Reason for Impact will be presented in a summary table and a data listing for ENR population.

## 10. DEMOGRAPHIC AND OTHER BASELINE CHARACTERISTICS

Demographic data and other baseline characteristics will be presented for the ENR population. No statistical testing will be carried out for demographic or other baseline characteristics. The following demographic and other baseline characteristics will be reported for this study:

- Age (years)
- Age Category (<40 Years, ≥40 Years, <60 Years, ≥60 Years)
- Sex
- Childbearing potential
- Race
- Hypertensive Medication status at Screening (Visit 1)

Page 24 of 46

NEB 5mg or RAM 5 mg Other BBs or CCBs

- Weight (kg)
- Height (cm)
- BMI (kg/m^2)
- Presence of Type 2 diabetes mellitus at Screening (Yes/No)
- Coronary Heart Disease (CHD) (Yes/No)
- Hypertension grade at Screening
- Presence of Hypercholesterolemia at Screening (with Hypercholesterolemia/ without Hypercholesterolemia)
- Mean sitting DBP at baseline (mmHg) selected arm (same dominant arm should be used throughout the study) component from vital sign page.
- Mean sitting SBP at baseline (mmHg) selected arm (same dominant arm should be used throughout the study) component from vital sign page.

#### 10.1. Derivations

• BMI  $(kg/m^2)$  = weight (kg)/ height  $(m)^2$ 

## 11. MEDICAL HISTORY AND PROCEDURES

Medical History information will be presented by for the SAF Population.

- Medical History data captured on eCRF form "Medical History/Concurrent Diseases" and for medical procedures on eCRF form "Medical Procedures" will be coded using Medical Dictionary for Regulatory Activities (MedDRA, Version 26. or latest) dictionary
  - Medical History conditions are defined as those conditions which were present prior to or at Screening.
  - o Presented by SOC and PT.

A separate listing for Medical Procedures information collected on eCRF form "Medical Procedures" will be presented by Monotherapy and combination therapy for the SAF Population.

